5.6 Supply, Packaging and Labelling

5.6.1 Supply

The study medication teverelix TFA will be provided by the Sponsor. The IMP will be manufactured, packed, labelled, and released by a qualified person and distributed under the responsibility of the Sponsor in accordance with the principle of Good Manufacturing Practice (GMP) and the applicable local regulations.

Teverelix TFA is supplied as a white powder to be reconstituted with 5% mannitol (w/v) in water for injection.

5.6.2 Storage

The study medication teverelix TFA has to be stored at $-20^{\circ}\text{C}\pm5^{\circ}\text{C}$. The diluent, mannitol, shall be stored at $+20^{\circ}\text{C}\pm5^{\circ}\text{C}$.

5.6.3 **Shipment**

The IMP will be shipped according to local regulations. The responsible investigator/responsible study personnel at the study site will confirm correct receipt of the IMP in writing and ensure it is stored safely and correctly. The investigator will document the distribution date and the amount used on the forms provided for this purpose.

5.6.4 Packaging

The packaging will be performed by the Sponsor according to GMP and all local legal requirements.

5.6.5 Labelling

The labelling will be performed by the Sponsor according to GMP and all local legal requirements. The labels will be written in the local language.

5.7 Blinding and Randomisation

Not applicable as this is an open-label study with regards to the administration of IMP.

[figure not shown]
5.8 **Prior and Concomitant Therapy**

Any concomitant therapies and medications administered during the study have to be documented. This also includes any non-medicinal treatment and hormonal contraception. The following details must be given: nature of the disease (indication), date of diagnosis, name of medicine (including active ingredient[s]) or specification of measures, dosage, route of administration and the dates of the start and end of the treatment.

5.8.1 Prohibited Previous and Concomitant Treatments

In line with the inclusion and exclusion criteria, during the study the use of the following drugs is prohibited:

- Antiarrhythmic medications
 - Class IA (e.g. quinidine, procainamide)
 - Class III (e.g. amiodarone, sotalol)

- Anti-androgen therapy (e.g. T replacement therapy, and 5α-reductase inhibitor treatment etc.) (Spironolactone is a permitted concomitant treatment)
- GnRH analogue or antagonists
- Androgen receptor antagonist
- Androgen synthesis inhibitors (e.g. abiraterone)
- Any other medication (e.g. 5-alpha reductase inhibitors) or herbal product (e.g. St. John's wort) that may affect hormone levels and might, therefore, confound interpretation of study results
- Finasteride and dutasteride within 12 weeks and 25 weeks, respectively, prior to screening

5.8.2 Admissible Concomitant Treatments

All other medicines, as well as over-the-counter medicines, apart from those mentioned in the prohibited treatments are allowed provided they do not affect the primary endpoint or integrity of this study.

This applies also specifically to following treatment options for prostate cancer:

- Prostate surgery
- Radiation therapy (discuss with Antev medical monitor prior to inclusion)
- Chemotherapy
- Cryotherapy
- Immunotherapy

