- If the QTcF interval is 450-480 msec, inclusive, in a participant with current use of medications with known effects on QT interval, the participant may be enrolled in the study following discussion with the Medical Lead

Note: Cardiac arrhythmia grading:

- o Bradyarrhythmias (HR <60/min)
- o Tachyarrhythmias (HR >100/min)
- o Supraventricular arrhythmias arrhythmias that originate in the sinoatrial node, atrial myocardium or atrioventricular node (regular QRS complex)
- o Ventricular arrhythmias arrhythmias that originate below the atrioventricular node (wide QRS complex)
- 10. Has known or suspected severe renal impairment
- 11. Has a medical history of diagnosis of, or treatment for, another malignancy within 2 years before the first dose of IMP, or previous diagnosis of another malignancy with

Page 36 of 84

- evidence of residual disease. Participants with nonmelanoma skin cancer or carcinoma in situ of any type are not excluded if they have undergone complete resection
- 12. Is currently using Class IA (e.g. quinidine, procainamide) or Class III (e.g. amiodarone, sotalol) antiarrhythmic medications
- 13. Has uncontrolled hypertension despite appropriate medical therapy (sitting BP of >180 millimetres of mercury [mmHg] systolic and >95 mmHg diastolic at 2 separate measurements taken no more than 60 minutes apart during the screening visit). Participants with isolated systolic BP measurements >180 mmHg may be rescreened. Participants with isolated systolic BP measurements 141 to 180 mmHg or isolated diastolic BP measurements ≥95 mmHg, although eligible, should be referred for further management of hypertension if indicated
- 14. Has known, previously diagnosed human immunodeficiency virus (HIV) infection, active chronic hepatitis B or C, life-threatening illness unrelated to prostate cancer, or any serious medical condition that could, in the investigator's opinion, potentially interfere with participation in this study. Specific screening for chronic viral illness is at the discretion of the site and/or local Institutional Review Board (IRB)
- 15. Has been exposed to another investigational drug within the 3 months prior to screening
- 16. Has anticipated non-availability for study visits/procedures
- 17. Plans to undergo surgery during the study period
- 18. Known presence of hepatic metastases

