First time LH levels falling below castration level (LH <1.1 U/L) will be defined as the analysis event. Analysis will be done from Day 1 to the end of the study.  
The following censoring rules will be used for this analysis:
  - Patients who did not achieve castration LH level during the study period will be censored at their last LH level assessment.
  - Patients who leave the trial without achieving castration LH level will be censored at their last LH level assessment.
12. Time to (first) overstep of LH castration level after achieving castration will be analysed using the Kaplan-Meier method. First time overstep of LH castration level will be defined as the analysis event. Analysis will be done from day of achieving castration LH level to the end of the study. Only patients who achieved castration LH level will be analysed for both ITT and PP Population. Day of achieving castration LH level will be defined as Day 1 for this analysis.  
The following censoring rules will be used for this analysis:
  - Patients with stable LH level will be censored at their last available measure.
  - Patients who leave the trial for reasons other than a non-castrate serum T level will be censored at their last LH assessment.
13. Changes from baseline in PD parameters over time will be analysed as mentioned in Section 5.1.2 for both ITT and PP Population.
14. Confirmed PSA Response Rate will be analysed as mentioned Section 5.1.2 for both ITT and PP Population  
*Note: Confirmed PSA Response rate is defined as patients who have a > 50% reduction at day 14 followed with confirmation at day 28*
15. PSA Response Rate at day 28 will be analysed as mentioned Section 5.1.2 for both ITT and PP Population
16. Number of participants with a PSA response of ≥50% reduction at the Day 168 visit will be analysed as mentioned in Section 5.1.2 both ITT and PP Population.
17. Number of participants with PSA response of ≥80% reduction at the Day 168 visit will be analysed as mentioned in Section 5.1.2 for both ITT and PP Population.
18. Percent change from baseline in serum PSA concentration at each visit will be analysed as mentioned Section 5.1.2 for both ITT and PP Population.

---

Document:

C:\ProgramData\activePDF\Temp\DocConverter\API\Input\\$651f4dc0b253\$FE3041C5883446E892B20AB6D3F0E1BD.docx

Author: [name]

Version and Date: Version 1.0, 21 Apr 2023

Page 61 of 66

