**Sensitivity Analyses on Supplementary FDA Recommended Efficacy Analyses**

Two sensitivity analysis will be performed. In the first sensitivity analysis the definition of treatment failures will be expanded and include following patients as treatment failures (patients with event):

1. Patients who did not achieve castrate serum T levels (<0.5 ng/mL or 1.73 nmol/L) by Day 28.
2. Patients who successfully achieve a castrate serum T level by Day 28 but fail to maintain it throughout the treatment period.
3. All the patients who leave the trial will be considered to have had an event at their last serum T level assessment.
4. Patients with two or more consecutive missing T levels (regardless of T levels before and after those missing time points). They will be considered to have had an event at the first missing time point.

In the second sensitivity analysis the ITT population will be changed to the population of patients who have received any dose of IMP and have a non-missing central lab serum T record at Day 28 except for patients who received concomitant medications and herbal supplements that could possibly affect T levels.

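### The PSA analyses have no rule for values taken after other prostate-cancer treatment, which the plan conditionally admits, so PSA falls after it count as teverelix effect

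*Protocol*

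**What the plan says.** Protocol 5.8.2, repeated in SAP 4.3.6.2, permits medicines that are not on the prohibited list; they "are allowed provided they do not affect the primary endpoint or integrity of this study". It continues: "This applies also specifically to following treatment options for prostate cancer", and lists prostate surgery, radiation, chemotherapy, cryotherapy and immunotherapy. The radiation entry reads "Radiation therapy (discuss with Antev medical monitor prior to inclusion", which asks for a conversation and is not a ban. Separately, exclusion criterion 17 in Protocol 4.2 bars a man who "Plans to undergo surgery during the study period".

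The effect of teverelix on PSA is a secondary objective (Protocol 2, SAP 2.1.2). SAP 6.8.2 analyses PSA in items 14 to 22, in both the ITT and PP sets. Item 16 is typical: "Number of participants with a PSA response of ≥50% reduction at the Day 168 visit". Item 17 does the same at 80%, item 18 is percent change, and items 21 and 22 are nadir and time to nadir. The nadir is each man's lowest PSA up to Day 168, with no restriction on which results qualify.

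For testosterone the SAP does take account of other therapy. SAP 3.5 and the second sensitivity analysis in SAP 6.8.3 use a population that keeps everyone "except for patients who received concomitant medications and herbal supplements that could possibly affect T levels".

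Other therapy is recorded with start and end dates. Protocol 5.8 says of that record: "This also includes any non-medicinal treatment and hormonal contraception".

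**The concern.** The condition on admissible treatment protects testosterone at Day 28 and something called integrity that neither document defines. It does not name PSA. Yet the listed treatments act on the tumour and can lower PSA by themselves, whatever teverelix is doing.

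The study is uncontrolled and judged on within-group change. No comparator arm shows how much of a PSA fall comes from other treatment. If a man starts radiotherapy or chemotherapy on study and his PSA then falls, the plan as written counts that fall in the response rate, the percent change and the nadir. What is at stake is how the PSA results are read, not the primary conclusion.

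**Working it through.** **The plan's own figure.** No PSA endpoint has a stated expected rate, power or threshold. The only sized endpoint is testosterone at Day 28 (Protocol 8.1.12): 74.5% against 90%, two-sided 5%, 80% power with 50 men, 60 enrolled at 16% dropout. By the normal approximation, (0.155 − 1.960 × √(0.745 × 0.255/50)) / √(0.90 × 0.10/50) = 0.806, which is 79.0% power; 50/0.84 = 59.5, rounded up to 60. These figures reproduce and do not bear on PSA.

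**Does any existing rule catch PSA after other treatment?**

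| Provision | What it covers | Reaches this case? |
|---|---|---|
| SAP 4.3.3, exclusion from analysis sets | Prohibited medication | No; the listed treatments are admissible |
| SAP 3.5 and 6.8.3, second sensitivity analysis | Therapies that may affect testosterone | No; nothing for PSA |
| SAP 5.3.1 | Missing efficacy data, not replaced | No; these values are present |
| SAP 3.7 and Protocol 8.1.1, data review of major violations | PP set only | Possibly, but no written criterion; ITT unaffected |
| Protocol 4.3, withdrawal | Failing efficacy with progression; illness that affects assessment | Some men only |
| SAP 6.6 | Medication tables by ATC code | Describes no count of surgery, radiation or cryotherapy |

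None of items 14 to 22 adds a rule of its own. That PSA values after other treatment are used follows from this absence and from the unrestricted nadir definition; no sentence says so outright.

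**Which items are exposed.** Confirmed response (Day 14, then Day 28) and Day 28 response leave little time for a newly started treatment to act. The exposure lies mainly in items 16, 17, 18, 21 and 22.

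**Size.** The documents give neither the PSA response rate nor the share of men treated, so both are assumed:
- p = response rate without other treatment
- f = share of men given other treatment, irrespective of response, all of whom then count as responders

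Reported rate = (1 − f)p + f = p + (1 − p)f, so the inflation is (1 − p)f.

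| p | f = 5% | f = 10% | f = 20% |
|---|---|---|---|
| 0.50 | 52.5% | 55.0% | 60.0% |
| 0.70 | 71.5% | 73.0% | 76.0% |
| 0.90 | 90.5% | 91.0% | 92.0% |

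Over this grid the inflation runs from 0.5 points (p = 0.90, f = 5%) to 10 points (p = 0.50, f = 20%).

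**Does removing treated men recover p?** Take 50 men, p = 0.70 and f = 10%. The planned analysis expects 45 × 0.70 + 5 = 36.5 responders, 36.5/50 = 73%. Without the 5 treated men it is 31.5/45 = 70%. Under these assumptions it does.

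**The case against.** The strongest reply is that exposure is limited. Planned surgery is excluded at entry, radiation is to be discussed with the medical monitor, and the integrity condition gives the sponsor a ground to refuse a treatment that confounds PSA. Men who fail on drug and progress must be withdrawn, so some would leave before Day 168. The secondary endpoints are exploratory and descriptive, no decision hangs on PSA, and treatment dates are recorded, so affected men could be found at reporting.

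Most of this stands, and it makes the point modest. It does not close the gap. No text says that a PSA effect triggers the integrity condition, unplanned surgery and the other four treatments remain possible, and a rule chosen at reporting is chosen after the data are seen.

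Three stronger readings are tempting and are not supported:
- **The bias always favours the drug.** The documents do not exclude a PSA rise after a procedure. Mainly in the drug's favour is as far as one can go.
- **A 10-point distortion is to be expected.** Suppose 40 of 50 men respond to the drug, and 5 of the 10 others, but none of the 40, receive further treatment and respond. The rate moves from 40/50 = 80% (Clopper-Pearson 66.3 to 90.0) to 45/50 = 90% (78.2 to 96.7). That is close to a worst case. With the same 10% treated irrespective of response, the shift is 0.20 × 0.10 = 2 points. A man who had already responded adds nothing.
- **Treated men should be counted as non-responders.** That penalises men who responded before starting other treatment. If 4 of the 40 responders were so treated, 80% would become 36/50 = 72%. It also differs from the testosterone analysis, which removes such men.

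**Conclusion.** The concern holds. The plan admits treatments that can lower PSA, guards only testosterone against other therapy, and has no rule for PSA after such treatment. In an uncontrolled study the PSA results, above all those at Day 168 and the nadir, can therefore include the effect of other treatment, mostly to the drug's advantage.

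The size cannot be known from the documents. The 3-point illustration rests on an assumed 70% response rate, 10% of men treated irrespective of response, and all treated men responding. If no man was treated, the bias is zero.

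A reader might infer that the primary result or the sample size is compromised. Neither is: both rest on testosterone. This is a gap in a secondary, descriptive analysis that should be closed before database lock.

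**What to change.** Keep the planned PSA analyses and add to SAP 6.8.2:

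1. A count of men who received any treatment listed in SAP 4.3.6.2 on study, by type, with start dates.
2. A pre-specified sensitivity analysis of the PSA endpoints that drops PSA values after the start of such treatment. Nadir and time to nadir are cut off at that date. For the Day 168 response rates, men who started such treatment before their Day 168 sample leave both numerator and denominator, as SAP 3.5 does for therapies affecting testosterone. Men whose other treatment was ongoing at Day 0 are left out of this sensitivity analysis.
3. A statement that the repeat is not produced if no man is affected, as SAP 3.5 already provides when its set equals the ITT set.

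Separately, Protocol 5.8.2 (prostate surgery admissible) and exclusion criterion 17 (planned surgery excluded) must be reconciled, with SAP 4.3.6.2 and 4.3.3 to match.

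The cost is one SAP paragraph and one extra set of PSA tables, using dates already collected. The denominator is slightly smaller and the PSA rate may be less favourable. If treated men tend to be the poorer responders, leaving them out does not remove all upward bias, which is why the count should be shown beside the result.

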5.9 Treatment Compliance and Drug Accountability

The reconstitution of the IMP will be prepared by the investigator or by study personnel assigned by the investigator. The IMP will be administered by the investigator to the participants according to the study protocol.

The investigator will ensure that the provided IMP will only be used within the framework of this study and as directed by the study protocol.

IMP accountability must be documented at each site and will be checked by a study monitor. All used and unused IMP will be collected by the study monitor and returned to the Sponsor upon completion of the study. Receipt, distribution, and return of the IMP must be documented according to study-specific instructions provided separately.

5.10 Safety Monitoring for Allergic Reactions

To ensure subject safety, investigators must be able to diagnose and treat immediate hypersensitivity reactions, including anaphylaxis. Medication and equipment necessary to treat immediate hypersensitivity reactions, including anaphylaxis must be available at the study centre. Subjects will be observed during drug administration and for at least 30 minutes following the injection for fever, chills, or other administration-related reactions. Should an immediate hypersensitivity reaction associated with hypotension and/or syncope occur, appropriate supportive measures (e.g., leg elevation; oxygen administration; intravenous fluids; and, medications such as epinephrine, antihistamines and corticosteroids, alone or in combination) will be employed, in accordance with standard emergency procedures of the study centre.

5.11 Management of Drug Overdose

No consequences are to be expected in case of drug overdose.

NTEV

6 Variables and Methods

6.1 **Population Characteristics**

6.1.1 **Demography**

The following demographic characteristics will be documented in the eCRF:

- Year of birth
- Age
- Weight and height
- Body mass index (BMI)

6.1.2 **Medical History**

General medical history findings in the past 5 years, considered relevant to the study by the investigator, will be documented in the eCRF together with the respective dates and periods (it should be indicated whether the condition is a past or an ongoing disease/illness at study entry). Relevant findings include, but may not be limited to, major surgeries, heart diseases, respiratory diseases, central nervous system and neurological diseases, psychiatric disorders, blood disorders, hepatorenal disorders, genitourinary disorders, and known allergies.

6.1.3 Prostate Cancer Diagnosis

Details of the underlying condition will be documented in the eCRF, including:

- Type of adenocarcinoma of the prostate
 - Metastatic
 - Non-metastatic
 - Hormone-sensitive
 - Non-curative
- Date of first diagnosis
- Presence of metastases (body region)
- Clinical signs and symptoms

6.1.3.1 **Primary Tumor, Lymph Node and Metastasis Classification of Prostate Cancer** Table 5 presents the Primary Tumor, Lymph Node and Metastasis (TNM) classification of primary tumours.

Page 43 of 84

_Tabl	e 5: TNM Classification of Primary Tumours [13]
_Clini	cal (cT)
TX	Primary tumour cannot be assessed
_T0	No evidence of primary tumour
_T1	Clinically inapparent tumour not palpable or visible by imaging
T1	Tumour incidental histologic finding in ≤5% of tissue resected (at time of
_a	transurethral resection of the prostate [TURP])
T1	Tumour incidental histologic finding in >5% of tissue resected (at time of TURP)
_ b	
T1c	Tumour identified by needle biopsy (because of elevated PSA level)
T2	Tumour confined within prostate
	Note: Tumours found in 1 or both lobes by needle biopsy but not palpable on
	digital rectal examination or reliably visible by imaging are classified as T1c)
T2	Tumour involves one-half of 1 lobe or less
a	
T2	Tumour involves more than one-half of 1 lobe but not both lobes
b	
T2c	Tumour involves both lobes
T3	Tumour extends through the prostatic capsule
	Note: invasion into the prostatic apex, or into—but not beyond—the prostatic
	capsule is classified as T2
T3	Extracapsular extension (unilateral or bilateral)
a	
T3	Tumour invading seminal vesicle(s)
b	
T4	Tumour fixed or invades adjacent structures other than seminal vesicles (e.g.
	bladder, levator muscles, and/or pelvic wall)
	E Primary Tumor, Lymph Node and Metastasis
Table	e 6 presents TNM classification of regional lymph nodes.
Tabl	e 6: TNM Classification of Regional Lymph Nodes (N) [13]
Clini	cal (cN)

Clinical (cN)	
NX	Regional lymph nodes were not assessed
N0	No regional lymph node metastasis
N1	Metastasis in regional lymph node(s)

TNM= Primary Tumor, Lymph Node and Metastasis

Table 7 presents TNM classification of distant metastasis.

Table 7: TNM Classification of Distant Metastasis (M)^a [13]

Clinical (cM)	
M0	No distant metastasis
M1	Distant metastasis
M1a	Non-regional lymph nodes(s)
M1b	Bone(s)
M1c	Other site(s) with or without bone disease

Page 44 of 84

TNM= Primary Tumor, Lymph Node and Metastasis

^a If more than 1 site of metastasis is present, use the most advanced category

6.1.3.2 Gleason Score

The Gleason score is the grading system used to determine the aggressiveness of prostate cancer. Gleason grades range from 1 to 5 and describe how much of the cancer from a biopsy looks like healthy tissue (lower score) or abnormal tissue (higher score). Most cancers score a Grade 3 or higher [14].

Since prostate tumours are often made up of cancerous cells that have different grades, 2 grades are assigned for each participant. A primary grade is given to describe the cells that make up the largest area of the tumour and a secondary grade is given to describe the cells of the next largest area. These numerical values are added to calculate the Gleason score (see Table 8 and Figure 2).

For instance, if the Gleason score is written as 3 + 4 = 7, it means most of the tumour is Grade 3 and the next largest section of the tumour is Grade 4, together they make up the total Gleason score. If the cancer is almost entirely made up of cells with the same score, the grade for that area is counted twice to calculate the total Gleason score.

Typical Gleason scores range from 6–10 (Table 8) The higher the Gleason score, the more likely that the cancer will grow and spread quickly. Each specimen is assigned 2 grades based on the most common and second most common pattern.

[figure not shown]

Figure 2: Gleason Score

Page 45 of 84

Table 8: Gleason Scoring System

Grade Group	Gleason Score	Gleason Pattern(s)
1	≤6	≤3 + 3
2	7	3 + 4
3	7	4 + 3
4	8	4+4(3+5/5+3)
5	9 or 10	4+5,5+4,5+5

